5.3 Intra-Operative Exclusion Criteria (Surgical Complications)

If any of the following surgical complication occurs during cataract surgery, the study subject will be discontinued from the study (see [Section 5.5.2.2](#) regarding handling of discontinued study subjects), have their study punctal plug removed and excluded from further participation in the study:

1. Sulcus-sulcus or bag-sulcus fixation
2. Posterior capsular rupture or zonular dialysis
3. Disruption of anterior hyaloids face
4. Vitreous loss
5. Capsulorhexis tear
6. Floppy iris syndrome

7. Requirement for the use of trypan blue, capsular tension ring or other intraocular device other than the IOL
8. Inability to place IOL in capsular bag
9. Significant anterior chamber hyphema
10. Zonular rupture.

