5.5 Study Subject Withdrawal or Termination Criteria

Each study subject will be informed that they are free to withdraw from the study at any time. The Investigator, the Investigator in consultation with the Medical Monitor, or the Medical Monitor may exercise his or her medical judgment to terminate a study subject's participation in the study if it is in the best interest of the study subject. A terminated study subject will be followed through Day 14 or until the condition has resolved or has become medically stable.

Medical Monitoring for this study will be conducted by:

[name]
Phone (Office): [contact]
Phone (Cell): [contact]
Email: [contact]

The name of the Medical Monitor and contact information will be provided to each study site.

Mati Therapeutics Inc. reserves the right to terminate the study at any time. Every effort will be made to collect all data required by the protocol during or following the study subject's early termination visit.

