5.5.1.1 Reason for Termination

A study subject will be terminated from the study if in the Investigators medical judgment, it was in the best interest of the study subject that developed or reported: a) moderate to severe signs or symptoms of ocular inflammation or pain, b) reported a serious AEs, regardless of relation to the study drug/device or has died.

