5.5.1.2 Reason for Discontinued

A study subject will be discontinued from the study if the Investigator is unable to insert a punctal plug in to the study subject's lower punctum, they have experienced a complication (intra-operative exclusion criteria) during surgery, the punctal plug has been extruded after the surgical visit (Visit3), study subject has used a prohibited concomitant therapy, is non-compliant, has missed scheduled study visits, has personal reasons, has relocated out of the area or has a desired to withdraw from further participation in the study in the absence of a medical need as determined by the Investigator. Other reason – the study subject was discontinued for a reason other than those listed above, the Investigator must specify the reason

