5.5.2 Handling of Study Subject Termination, Discontinued or Disqualified

5.5.2.1 Handling of Terminated Study Subject

A terminated study subject will return to the clinic for an end of study safety evaluation and the removal of the masked punctal. A terminated study subject will receive appropriate treatment at the discretion of the Investigator. Notification of termination will be clearly documented on the appropriate Case Report Form. A terminated study subject is considered to have completed the study and **will NOT be replaced**.

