5.5.2.2 Handling of Discontinued Study Subject

A study subject may voluntarily discontinue (withdraw) from the study at any time they choose. Notification of discontinuation will be clearly documented on the appropriate Case Report Form. If a study subject elects to withdraw from the study during the study follow-up period, the Investigator will make every effort to have the study subject return to the clinic for an end of study safety evaluation and the removal of the masked punctal plug. A study subject who is discontinued from the study **will be replaced**.

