7.4.3 Visit 3: (Surgical Visit, Day 0)

Cataract surgery (e.g., corneal incision, anterior capsulotomy, fragmentation/removal of the lens/cataract) may be performed with the assistance of a femtosecond laser. It is recommended the surgeon use a standard phacoemulsification extraction surgical technique. The anterior capsulotomy should be a well centered continuous curvilinear capsulorhexis approximately 5.5 mm in diameter and the lens must be placed in the capsular bag. A viscoelastic should be used to protect the endothelium. At this visit the following surgical data will be recorded:

- a. Surgical Eye Pupil measurements (prior to and immediately following surgery)
- b. Monocular cataract extraction/IOL implantation recording the following information:
 - Indicate the incision Type (clear cornea, limbal, sclera), Location (nasal, temporal, superior, other) and Size (mm)
 - Nucleus removal time (< 1min, 1 - < 2 min, 2 - < 3 min, 3 - < 4 min, >4 min)
 - Ease of Cortex removal (Very Easy, Easy, Difficult, Very Difficult)
 - Effective Phaco Power (recording of phaco time and power)
 - Type of IOL (e.g., monofocal, toric, etc.) and lens power
 - Record any surgical complications
- c. Visual Inspection of the masked punctal plug at the conclusion of surgery
- d. Subject reported AEs prior to or after surgery
- e. Concomitant medication

Should a surgical complication occur, implantation of the lens will be at the Investigator's discretion. If any of the surgical complications occur, as listed in [Section 5.3](#), the study subject's punctal plug will be removed after surgery and the subject terminated from the study.

Pre-, intra- and post-operative open-label medications will be used as is customary for the Surgeon/Investigator, and should be consistent for all cases. All pre-, intra- and post-operative open-label medications must be recorded on the Concomitant Medication CRF. However the use of any pre-, intra- or post-operative NSAID or corticosteroid is prohibited, with the exception of a subject who has been prescribed and has been taking a baby aspirin (≤ 81 mg/daily). An LRI or AI procedure required for any sphere/cylinder correction before, during or after cataract surgery is prohibited during the study period.

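### Section 7.4.3 terminates a subject with a listed surgical complication, while 5.3, 5.5.1.2 and 5.5.2.2 discontinue and replace that subject; separately, 10.1 and 10.4.2 define the ITT set differently

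*Combined protocol and SAP*

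**What the plan says.** **Status after a surgical complication.** Section 5.3 lists ten intra-operative events and opens: "If any of the following surgical complication occurs during cataract surgery, the study subject will be discontinued from the study". It points to 5.5.2.2 for handling, requires plug removal and bars further participation. Section 5.5.1.2 includes among the reasons for discontinuation that "they have experienced a complication (intra-operative exclusion criteria) during surgery". Under 5.5.2.2, "A study subject who is discontinued from the study" is to be replaced.

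Section 7.4.3, on the surgical visit, refers to the same 5.3 list but says that the "punctal plug will be removed after surgery and the subject terminated from the study". Section 5.5.2.1 then applies: "A terminated study subject is considered to have completed the study", and is not replaced. Section 4.2 ends the study when 75 subjects have either reached Visit 7 or been terminated. The reasons for termination in 5.5.1.1 are "moderate to severe signs or symptoms of ocular inflammation or pain", a serious adverse event, or death.

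**Analysis set.** Section 10.1 defines the primary ITT population as randomised subjects with at least one completed post-operative follow-up visit and no major protocol violation. It gives violation of the inclusion/exclusion criteria as one example and says that such subjects or visits may be excluded. Section 10.4.2 puts all data from every subject with at least one post-operative pain evaluation into the ITT set, and drops significant deviations only from the per-protocol set.

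**The concern.** Terminated and discontinued are defined categories here, with opposite replacement rules that the protocol prints in bold. One event falls into both. Staff at the surgical visit may well be working from 7.4.3, and the protocol states no order of precedence. A site that follows 7.4.3 keeps the subject in the count of 75 and enrols nobody in their place. A site that follows 5.3 does the reverse. With up to three sites, practice could differ within the trial.

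These subjects are already randomised and exposed, because the plug goes in 1 to 2 days before surgery (6.1.4). Their place in the efficacy set should therefore follow from a stated rule. With two ITT definitions in force, it is left to the evaluability assessment in 10.6.3, which gives no criteria. That assessment precedes the code break at database lock. However, 10.4.7 unmasks data at an interim analysis once at least 25 subjects have completed Visit 7, so a rule written in advance is safer.

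**Working it through.** **1. Status, section by section**

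| Section | Status for a 5.3 complication | Consequence |
|---|---|---|
| 5.3 | discontinued | sends the reader to 5.5.2.2 |
| 5.5.1.2 | discontinued | complication named as a reason |
| 5.5.2.2 | (rule for discontinued) | replaced |
| 7.4.3 | terminated | – |
| 5.5.2.1 | (rule for terminated) | counted as completed, not replaced |
| 4.2 | (rule for terminated) | counts towards the 75 |
| 5.5.1.1 | complication not named | – |

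Sections 5.3, 5.5.1.2 and 5.5.2.2 form one consistent path. Section 7.4.3 stands alone, and the list of termination reasons does not support it.

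**2. Effect on numbers.** The plan's own figure reproduces: 25 blocks × 3 = 75 lines, 50 active and 25 placebo, matching the example numbers 101–175 in 10.6.1. The documents give no complication rate, so I assume a rate c.

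- Replaced: randomise 75/(1 − c), rounded up.
- Not replaced: 75 × (1 − c) remain free of a complication.
- Chance of at least one case in 75: 1 − (1 − c)^75.

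| Assumed c | Randomised if replaced | Free of complication if not replaced | Chance of at least one case |
|---|---|---|---|
| 2% | 77 | 73.5 | 78% |
| 5% | 79 | 71.3 | 98% |
| 10% | 84 | 67.5 | over 99% |
| 15% | 89 | 63.8 | over 99% |

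For scale, take the Day 1 pain-free rates cited in 2.1 for the 0.1% drops, about 80% against 50%. The plan names no test and has no power calculation, so this is illustrative. I use the normal approximation for two proportions, with pooled variance under the null. At 50 v 25:

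- null SE = √(0.7 × 0.3 × (1/50 + 1/25)) = 0.1122
- alternative SE = √(0.16/50 + 0.25/25) = 0.1149
- power = Φ((0.30 − 1.96 × 0.1122)/0.1149) = 75.7%

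With both arms shrunk by c and no replacement, power is 74.9%, 73.6%, 71.3% and 68.9% at 2%, 5%, 10% and 15%.

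**3. The two ITT definitions**

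- *No post-operative evaluation* (for example, exit on the day of surgery): out under 10.1, which needs a follow-up visit, and out under 10.4.2, which needs a follow-up pain evaluation. The sections agree.
- *At least one post-operative evaluation, complication not classed as a violation*: in under both, provided the evaluation came from a visit that 10.1 counts as follow-up.
- *At least one post-operative evaluation, complication classed as a criteria violation*: may be excluded under 10.1, included under 10.4.2. The sections differ.

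The second and third cases can arise. Section 5.5 says that a terminated subject will be "followed through Day 14 or until the condition has resolved or has become medically stable", and the Early Exit Visit (7.4.6) records pain. Neither 10.1 nor 10.4.2 says whether an Early Exit Visit counts as follow-up. Section 7.4.1 groups 5.3 with the inclusion/exclusion criteria, which makes the third classification possible.

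**4. Size if a few eyes are left out.** Assume 2% to 6% of 50 active eyes, which is 1 to 3, all in pain on Day 1, and none removed on placebo. From 40/50 = 80%, the active rate becomes 40/49 = 81.6%, 40/48 = 83.3% or 40/47 = 85.1%, a shift of 1.6 to 5.1 points against a cited difference of about 30. Half of 25 is not a whole number, so I use placebo 13/25 and 12/25. Two-sided Fisher p for 40/50 and then 40/47 is 0.017 and 0.004 with 13/25, and 0.007 and 0.002 with 12/25. A borderline case can be built: 38/50 against 38/47 gives 0.064 and 0.015 with 13/25. With 12/25 it gives 0.021 and 0.007, so the crossing of 0.05 depends on rounding the placebo rate.

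**The case against.** The conflict comes close to resolving itself. Section 7.4.3 sends the reader to 5.3, whose first sentence says discontinued and points to 5.5.2.2. That is fair, and it shows which word is wrong. It does not remove an instruction in force, because 7.4.3 still names the other category.

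On the analysis set, a reader might infer that 10.1 and 10.4.2 give opposite answers for complication subjects. The documents do not go that far. Neither section mentions surgical complications. Since 5.3 prescribes how the event is handled, a subject handled that way has followed the protocol. A subject who leaves on Day 0 without an evaluation is out under both sections. What stands is the general mismatch between the two ITT definitions, which touches any subject with a deviation.

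A reader might also infer that neither status secures follow-up because both lead only to a closing safety visit. For terminated subjects, 5.5.2.1 does say that they "will return to the clinic for an end of study safety evaluation", alongside the longer follow-up in 5.5. The similar sentence in 5.5.2.2 covers subjects who elect to withdraw during follow-up, so it cannot be read across to discontinuation at surgery.

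The figures are illustrations. The rates are assumed, and 47 active eyes would not be the planned comparison if removed subjects were replaced. The absence of spare lines on the 75-line list follows from every replacement under 5.5.2.2 and 5.5.2.3, not from this issue alone.

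**Conclusion.** The status conflict is certain from the text, and 7.4.3 is the section to correct. The choice of word decides who is replaced and who counts towards the 75. The analysis-set point holds in the narrower form: 10.1 and 10.4.2 state two ITT definitions, and complication subjects are caught between them only if they have a post-operative evaluation and the complication is classed as a criteria violation.

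The effect is probably small: about 2 to 4 randomised subjects at assumed rates of 2% to 5%, and roughly 1 to 2 points of illustrative power. A reader might infer a biased treatment comparison. That would need complications, or the way they are classed, to differ by arm, and nothing in the documents suggests either. Safety data are not at risk: 10.4.4 keeps every exposed subject in the safety set, and 8.7 follows adverse events until they resolve or are stable. The correction is worth making because it costs almost nothing and the event is likely to occur at least once (78% at an assumed 2%).

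**What to change.** **Required**

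- In 7.4.3, replace terminated with discontinued, so that replacement and the count towards 75 follow 5.3, 5.5.1.2 and 5.5.2.2.
- In 10.1, define the ITT set as 10.4.2 does: deviations are removed only from the per-protocol set.
- Add one sentence: a 5.3 complication handled as prescribed is not a protocol violation, and any such subject with a post-operative evaluation is analysed as randomised.

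The cost is one word, one revised definition and one added sentence, with no new data or visits.

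**Optional.** The sponsor could collect the Visit 4 to 7 pain and cells/flare assessments after plug removal, where the subject agrees. This is a design choice with a price: up to four visits each for a few subjects, and dilution. If retained active eyes respond at the 50% placebo rate, the active rate falls from 80% to 79.4%, 78.8% or 78.2% at 2%, 4% or 6% complications (for example, 0.98 × 80% + 0.02 × 50% = 79.4%). Exact Fisher power at 50 v 25 then falls from 69.1% to 66.9%, 64.7% or 62.5%. Fisher's test is more conservative than the approximation used above, hence the lower starting figure. If this option is taken, a sensitivity analysis without these eyes would show the undiluted result.

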5.4 Strategies for Recruitment and Retention

To increase study subject enrollment and retention in the study, sites should dedicate an individual [Clinical Research Coordinator (CRC)] who is well informed regarding the study design, required inclusion/exclusion criteria and visit schedule, as the main contact who is readily available to answer all potential subject questions and/or concerns about participating in the clinical study. The CRC should be prepared to discuss with a potential study subject the differences in the amount of time, examination procedures and visit schedule they would experience if they agreed to participate in the study. In addition, should a subject agree to participate in the study, the CRC would be readily available and their main contact person while participating in the study.

To encourage recruitment and retention of a study subject, sites should offer a subject reimbursement for transportation cost and a stipend for their time and effort for participation, offer less waiting time in the doctor's office by scheduling more flexible and reliable appointment times. In addition, discuss the advantages of participating in the study by not having to remember or instilling one less drop prior to or after cataract surgery.

5.5 Study Subject Withdrawal or Termination Criteria

Each study subject will be informed that they are free to withdraw from the study at any time. The Investigator, the Investigator in consultation with the Medical Monitor, or the Medical Monitor may exercise his or her medical judgment to terminate a study subject's participation in the study if it is in the best interest of the study subject. A terminated study subject will be followed through Day 14 or until the condition has resolved or has become medically stable.

Medical Monitoring for this study will be conducted by:

[name]
Phone (Office): [contact]
Phone (Cell): [contact]
Email: [contact]

The name of the Medical Monitor and contact information will be provided to each study site.

Mati Therapeutics Inc. reserves the right to terminate the study at any time. Every effort will be made to collect all data required by the protocol during or following the study subject's early termination visit.

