4.2 Study Endpoints

The study will be complete when 75 study subjects (75 eyes) have been evaluated at Visit 7 (Day 14 post-op) or have been terminated from the study.

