7.4.5 Visit 7: (Final Study Visit, Day 14 ± 2 days Post-Op)

At the final scheduled study visit the following will be performed on the surgical eye only:

- a. Investigator evaluation of ocular pain

NOTE: The Investigator that interviewed and record the subject's response to ocular pain at Visit 4 (Day 1 post-op) should interview the subject at this visit

- b. Monocular Distance Visual Acuity (Uncorrected and Best-Corrected)
- c. Manifest Refraction
- d. Inspection of the masked punctal plug via the slit lamp
- e. Slit-Lamp examination

NOTE: The Investigator that performed slit-lamp evaluation at Visit 4 (Day 1 post-op) should perform the slit-lamp evaluation at this visit.

- f. Fundus examination
- g. Removal of the masked punctal plug
- h. Recording of any reported adverse event(s).
- i. Concomitant medication

An exit form will be completed at this final study examination (Visit 7), or whenever the study subject completes or leaves the study for any reason. The Investigator and/or his/her staff will review with each study subject the proper use or discontinuation of any post-op open-label medications prescribed by the Investigator. Any changes, discontinuation or addition of an open-label medication(s) must be recorded on the Concomitant Medication CRF.

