7.4.6 Early Exit Visit

Any study subject exiting the study early, the Investigator must remove the study subject's masked punctal plug. In addition, the Investigator should record the following:

- a. Investigator evaluation of ocular pain

NOTE: The Investigator that interviewed and record the subject's response to ocular pain at Visit 4 (Day 1 post-op) should interview the subject at this visit

- b. Monocular Distance Visual Acuity (Uncorrected and Best-Corrected)
- c. Manifest Refraction

- d. Inspection of the masked punctal plug via the slit lamp
- e. Slit-Lamp examination

NOTE: The Investigator that performed slit-lamp evaluation at Visit 4 (Day 1 post-op) should perform the slit-lamp evaluation at this visit.

- f. Fundus examination
- g. Removal of the masked punctal plug
- h. Recording of any reported adverse event(s).
- i. Concomitant medication

Any changes, discontinuation or addition of an open-label medication(s) must be recorded on the Concomitant Medication CRF.

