7.7 Prohibited Medications, Treatments and Procedures

7.7.1 Prohibited Medications

The use of any systemic, topical and/or ophthalmic NSAID or corticosteroid within 48 hours of Visit 2 or during the course of the study (Visit 2 to Visit 7) is not allowed unless medically necessary. If an NSAID, corticosteroid or an immunosuppressant is required for any condition (ocular or systemic), the study subject will be terminated from the study, have their masked punctal plug removed and will be followed through Visit 7 (Day 14) or if required until the condition has resolved or has become medically stable.

Investigational/experimental/off-label usages of drugs or devices are not permitted during the study, except as described in the protocol.

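### No text requires pain and cell/flare scoring at each remaining visit after termination for poor response, so the observed-data analysis may omit poor responders, mainly at Days 3 and 7

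*Combined protocol and SAP*

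**What the plan says.** **Termination.** Under Section 5.5.1.1 the investigator may, on medical judgment, terminate a subject who develops "moderate to severe signs or symptoms of ocular inflammation or pain". Under Section 5.5.2.1 that subject "will return to the clinic for an end of study safety evaluation and the removal of the masked punctal" plug, counts as having completed the study, and is not replaced. Section 4.2 calls the study complete when 75 subjects "have been evaluated at Visit 7 (Day 14 post-op) or have been terminated from the study".

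**Follow-up.** Section 5.5: "A terminated study subject will be followed through Day 14 or until the condition has resolved or has become medically stable". Section 7.7.1, for subjects needing an NSAID, corticosteroid or immunosuppressant, requires termination and plug removal and says the subject "will be followed through Visit 7 (Day 14) or if required until the condition has resolved" or stabilised. Section 7.9.1, on rescue, sets follow-up to Visit 7 or to resolution or stability.

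**Scoring.** For the Early Exit Visit, Section 7.4.6 says "In addition, the Investigator should record the following" and lists pain and the slit-lamp examination. Section 7.4.5 lists the same two among the Visit 7 procedures. Sections 5.5 and 5.6 carry a best-effort clause that begins "Every effort will be made to collect all data required by the protocol during or following the study" and goes on to the subject's early termination visit. Section 11.1 makes both scores source data at each visit.

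**Analysis.** Section 10.4.3 bases both efficacy endpoints on observed data, with last observation carried forward as an optional sensitivity analysis if much is missing. Section 10.1 lets subjects or visits be excluded for prohibited medication.

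**The concern.** The outcome can itself cause a subject to leave the scoring schedule. A subject who does badly may be terminated, is scored at exit, and then has no stated obligation to be scored again at the visits where the treatments are compared. An observed-data analysis takes whoever was scored, so the subjects missing at a later visit would tend to be those who responded poorly. The loss may be heavier on placebo if the drug works, and placebo has only 25 subjects.

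A second route reaches scores that were collected. A subject who needs a steroid or NSAID is terminated under Section 7.7.1, and Section 10.1 could then remove that subject, or those visits, for prohibited medication. No section says how scores after termination or rescue are to count.

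Scores that were never taken cannot be recovered at analysis.

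**Working it through.** The plan gives no termination rate, dropout rate or sample size calculation, so there is no stated figure to reproduce. The check is first textual, then arithmetic for scale.

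**Step 1. What is required, by route.**

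| Route | At exit or rescue | Remaining visits before Day 14 | Day 14 |
|---|---|---|---|
| Terminated for pain or inflammation, no NSAID or steroid (5.5, 5.5.1.1) | Pain and slit lamp (7.4.6) | Best effort only; no visit or score named | Follow-up may end at resolution or stability; no scores named |
| Terminated because an NSAID or steroid is needed (7.7.1) | Same | Not named | Visit 7 named, and 7.4.5 lists both scores; 10.1 may exclude them |
| Rescued within criteria (7.9, 7.9.1) | Not an exit; scheduled visits are not ended | On schedule, but the follow-up sentence does not say so | Same alternative of resolution or stability |

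The firm gap is therefore Days 3 and 7, plus Day 14 where the resolution-or-stability alternative applies.

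**Step 2. Scores at risk per subject.** Pain is scored at Days 1, 3, 7 and 14. With the exit score credited and no later scoring:

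- exit at Day 1: 3/4 = 75% uncollected
- exit at Day 3: 2/4 = 50%
- exit at Day 7: 1/4 = 25%

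For inflammation the counts are also 3, 2 and 1, out of four scores (synopsis, Visits 4 to 7) or out of three (Section 4.2.2, Days 3, 7 and 14). Where Visit 7 is kept under 7.7.1, one fewer is lost: 2, 1 and 0.

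**Step 3. Bound at any visit.** A missing subject could have been pain-free or not. In a by-visit proportion, as tabulated under Section 10.4.9, this is worth up to 1/25 = 4 points on placebo or 1/50 = 2 points on active. One missing in each arm widens the difference by up to 6 points.

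**Step 4. Direction if only placebo subjects in pain are lost.** Assume 10/25 or 12/25 placebo subjects pain-free, near the 38% and 46% vehicle rates in Section 2.1. Let k subjects still in pain be unscored. Observed rate = pain-free/(25 − k).

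| k | from 10/25 = 40.0% | from 12/25 = 48.0% |
|---|---|---|
| 1 | 10/24 = 41.7% (+1.7) | 12/24 = 50.0% (+2.0) |
| 2 | 10/23 = 43.5% (+3.5) | 12/23 = 52.2% (+4.2) |
| 3 | 10/22 = 45.5% (+5.5) | 12/22 = 54.5% (+6.5) |

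The placebo rate is 1.7 to 6.5 points too high, so the apparent drug effect shrinks by that amount.

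**Step 5. Equal loss fraction in both arms.** Let a fraction f of those not pain-free be unscored in each arm. Observed rate = p/(p + (1 − p)(1 − f)). For 86% against 46% and f = 50%: active 0.86/0.93 = 92.5%, placebo 0.46/0.73 = 63.0%, difference 29.5 points instead of 40. The protocol gives no Day 3 or Day 7 rates, so its Day 14 pairs and its Day 1 pair (Section 2.1) stand in.

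| True rates | f = 25% | f = 50% | f = 75% |
|---|---|---|---|
| 86% v 46% (40 points) | 35.9 | 29.5 | 18.8 |
| 84% v 38% (46 points) | 42.5 | 36.2 | 24.4 |
| 80% v 50% (30 points) | 27.1 | 22.2 | 14.1 |

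**Step 6. The reverse pattern.** If only active subjects in pain are lost, say 3 from 43/50 = 86.0%, the observed rate is 43/47 = 91.5% and the effect is overstated by 5.5 points. The direction is not fixed by the design.

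**The case against.** The strongest reply is that collection is already largely covered. Follow-up in Section 5.5 is worded as mandatory, the exit visit scores both outcomes, the best-effort clause reaches data after exit, and Section 11.1 expects both scores at each visit. A subject terminated for pain or inflammation would probably be given a steroid or NSAID, which brings in the Visit 7 follow-up of 7.7.1. Most of this stands for Day 14, and it narrows the gap. It does not close it: the best-effort clause names no visit or score, Section 11.1 covers visits that take place and does not require attendance, and nothing here names Visits 5 or 6.

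A reader might infer from Sections 5.5.2.1 and 4.2 that follow-up ends at a single exit evaluation. The documents do not say that. Section 4.2 defines when the study is complete, and the completed status in 5.5.2.1 leads into the rule against replacement. Both are compatible with an exit evaluation followed by further follow-up under 5.5. Nor does rescue within the criteria of 7.9.1 by itself take a subject off the schedule.

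It can also be said that counting terminated or rescued subjects as failures needs no later scores, since the exit form and medication record suffice. That is correct for a pain-free or responder analysis, and is part of the fix. It does not serve the pain severity of Section 10.4.2 or mean cell and flare scores. Carrying the exit score forward would act similarly for these subjects, but it is optional, has no defined trigger, and cannot show what happened after exit.

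Finally, post-rescue scores partly reflect prednisolone and may make rescued placebo subjects look improved. This stands, and is why such scores should not be relied on alone.

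**Conclusion.** The concern holds in a limited form. A site following the protocol exactly could stop scoring a subject terminated for poor response before the remaining visits, and the analysis would proceed without those scores. The gap is mainly Days 3 and 7, with Day 14 exposed where follow-up may end at resolution or stability. Scores after a 7.7.1 termination may also be excluded under 10.1 even when taken.

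The size is unknown. The bound of 4 points (placebo) or 2 points (active) per missing subject needs only the planned arm sizes. The 1.7 to 6.5 points in Step 4 rest on assumed rates near those quoted for Day 14, on one to three subjects lost from placebo alone, and on all of them still being in pain. Day 14 is also the best-covered visit, so these figures show scale and are not forecasts. A reader might infer that the gap flatters the drug; the illustrated patterns with loss mainly on placebo shrink its apparent effect, and only other patterns reverse that. The number of subjects may be small in this pilot, but the change is cheap and should be made.

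**What to change.** 1. **Section 5.5**, cross-referenced from 5.5.2.1 and 7.7.1: a terminated subject who has not withdrawn consent attends the remaining scheduled visits through Day 14 for pain and cell/flare scoring, regardless of plug removal or resolution. Each score is flagged as before or after rescue, steroid/NSAID use or plug removal. Make the same visits explicit in 7.9.1 for rescued subjects.
2. **Section 10.1**: subjects and visits are not excluded from the ITT set solely because of rescue or medically necessary steroid/NSAID use.
3. **Sections 10.4.2 and 10.4.3**: prespecify an analysis that counts subjects rescued, or terminated for pain or inflammation, as not pain-free or as non-responders from that point. Report it beside the observed-data analysis, and do not rest conclusions on post-rescue scores as observed alone.

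The cost is a wording amendment, one CRF flag, one extra analysis, and up to three short visits, already on the schedule, for a few subjects.
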